## List of Abbreviations and Definition of Terms

Abbreviation or Term	Definition/Explanation
AE	adverse event
ALP	alkaline phosphatase
ALT	alanine aminotransferase
AST	aspartate aminotransferase
AUC	area under the concentration-time curve
BLRM	Bayesian logistic regression model
B-NHL	B-cell Non-Hodgkin's Lymphoma
C max	maximum concentration
C min	minimum concentration
CMR	complete metabolic response
COO	cell-of-origin
CR	complete response
CRF	case report form
CRS	cytokine release syndrome
CTCAE	Common Terminology Criteria for Adverse Events
DLBCL	diffuse large B-cell lymphoma
DLRM	dose level review team meeting
DLRT	dose level review team
DLT	dose limiting toxicities
DOR	duration of response
ECG	electrocardiogram
ECOG	Eastern Cooperative Oncology Group
End of Follow-up	It is defined as when the last subject completes the last protocol-specified assessment in the study
End of Study (Individual Subject)	Defined as the last day that protocol-specified procedures are conducted for an individual subject (ie, the date the subject withdraws full consent from the study, completes the safety follow-up visit or long-term follow up [whichever is later] or death).
End of Study (primary completion)	The time when the last subject is assessed or receives an intervention for the purposes of final collection of data for the primary analysis.
End of Study (end of trial)	It is defined as when the last subject is assessed or receives an intervention for evaluation in the study (ie, last subject last visit), following any additional parts in the study (eg, LTFU).

Abbreviation or Term	Definition/Explanation
End of Treatment	Defined as the last assessment for the protocol-specified treatment phase of the study for an individual subject
FIH	first-in-human
ІСН	International Conference on Harmonisation
INR	international normalized ratio
IPD	Important Protocol Deviation
IV	intravenous
MRD	minimal residual disease
MTD	maximum tolerated dose
ORR	overall response rate
OS	overall survival
PD	progressive disease
PD	pharmacodynamics
PET-CT	positron emission tomography-computed tomography
PFS	progression-free survival
РК	pharmacokinetic
PMD	progressive metabolic disease
PMR	partial metabolic response
PR	partial response
PT	thromboplastin time
PTT	partial thromboplastin time
QTc interval	QT interval corrected for heart rate using accepted methodology
RP2D	recommended phase 2 dose
RR	respiratory rate
SD	stable disease
SFU	safety follow-up
LTFU	long-term follow-up
T max	time of maximum concentration
TPI	toxicity probability interval
ULN	upper limit of normal

#### 1. Introduction

The purpose of this Statistical Analysis Plan (SAP) is to provide details of the statistical analyses that have been outlined within the protocol **amendment 4** for study 20170533, AMG 562 dated Enter Date. **07 August 2019.** The original scope of this plan included the interim analyses, the primary analysis and the final analysis that were planned and would be executed by the Amgen Global Biostatistical Science department unless otherwise specified. The scope of the analysis has been restricted due to the discontinuation of the study earlier than planned. The key analyses to be performed have been identified by the study team and are outlined in this revised document.

## 2. Objectives, Endpoints and Hypotheses

#### 2.1 Objectives and Endpoints

Objectives	Endpoints	
Primary		

 
Evaluate the safety and tolerability of AMG 562 in adult subjects with relapsed / refractory DLBCL, MCL, or FL
 
Estimate the maximum tolerated dose (MTD) and/or a biologically active dose (eg, recommended phase 2 dose [RP2D])
 
	Incidence of dose limiting toxicities (DLTs), treatment-emergent adverse events, treatment-related adverse events, disease-related events and clinically-significant changes in vital signs, physical examinations, electrocardiograms (ECG) and clinical laboratory tests	
Secondary		
Characterize the pharmacokinetics (PK) of AMG 562	
 
AMG 562 PK parameters including, but not limited to, maximum concentration (Cmax), minimum concentration (Cmin), time of maximum concentration (Tmax), area under the concentration-time curve (AUC), and if feasible, half-life (t1/2)
 
	
Evaluate anti-lymphoma activity of AMG 562	
 
ORR according to Lugano classification
 
Best Overall response by category. [Response terminology reflects the response criteria used. The Lugano Classification response definitions for positron emission tomography-computed tomography (PET-CT) evaluations of fluorodeoxyglucose (FDG)-avid lymphomas uses the terminology complete metabolic response (CMR), partial metabolic response (PMR), no metabolic response (NMR), or progressive metabolic disease (PMD). Corresponding designations from earlier response criteria include complete response (CR), partial response (PR), stable disease (SD), or progressive disease (PD)]
 
Duration of response (DOR)
 
	

	Progression free survival (PFS)	
	Overall survival (OS)	
Exploratory		
Evaluate the formation of anti-AMG 562     antibodies	Incidence of anti-AMG 562 antibody     formation	

## 2.2 Hypotheses and/or Estimations

The maximum tolerated dose (MTD) or recommended phase 2 dose (RP2D) of AMG 562 will have an acceptable safety profile and evidence of anti-lymphoma activity in patients with relapsed and/or refractory B-NHL, specifically DLBCL, MCL, or FL as measured by the overall response rate (ORR) and rate of CR. No formal hypothesis testing will be performed, and all statistical analyses are descriptive.

## 3. Study Overview

## 3.1 Study Design

This is a multicenter, Phase 1, first-in-human (FIH), non-randomized, open-label study in adult subjects with relapsed / refractory DLBCL, MCL, or FL. AMG 562 will be administered weekly as short term IV infusions (1.5 hour).

The study will consist of up to a 21-day screening period, a treatment period, a safety follow-up (SFU) visit conducted 30 (+7) days after the last dose of AMG 562, and a long-term follow-up (LTFU) period that will begin after the SFU visit is completed. Subjects will be followed for response evaluation at week 5, week 15, week 25 and at end of treatment if end of treatment is at week 35 or beyond (± 3 days). Subjects who

stopped response evaluations will be followed every 3 months (± 2 weeks) for survival follow-up. The total duration of the LTFU will be up to 2 years from the first dose of AMG 562.

#### Treatment Holiday

Starting with cycle 4, a longer treatment holiday between cycles may be implemented on a per subject basis for individual treatment cycles after approval by the Amgen Medical Monitor (see Section 6.2.1.1. of protocol for details)

For subjects identified as having confirmed CR/CMR, investigators may choose to implement treatment-free intervals of 2-4 weeks ("Consolidation Phase"). For subjects remaining in CR/CMR at 12 months, treatment-free intervals may be increased to 8 weeks between cycles ("Maintenance Phase"). Treatment for these subjects can be continued until progression or at the discretion of the investigator. Treatment can be discontinued for patients remaining in CR/CMR at the discretion of the investigator.

This phase 1 study consists of two parts:

- Part 1 includes dose exploration to evaluate the safety and tolerability of AMG 562 as monotherapy in subjects with relapsed/refractory DLBCL, MCL, or FL.
- Part 2 is an evaluation of AMG 562 in a dose expansion group to gain further efficacy and safety experience with AMG 562 as monotherapy in subjects with DLBCL. Part 2 will start with a dose that is identified by the DLRT following estimation of the MTD/RP2D in Part 1.

#### Part 1: Dose Exploration

Up to approximately 30 subjects will be enrolled to the dose exploration cohorts to estimate the MTD, safety, tolerability, PK, and pharmacodynamics of different doses of AMG 562 in subjects with relapsed / refractory DLBCL, MCL, or FL. Dose exploration will be conducted in 2 stages using a Bayesian logistic regression model (BLRM) design to guide dose escalation. In the initial cohorts, single subjects will be enrolled at dose levels anticipated to be lower than the dose levels at which adverse events related to AMG 562 may be observed. Enrollment will proceed with multiple subject cohorts of 3 to 4 subjects per cohort when higher dose levels are open for enrollment by the Dose Level Review Team (DLRT) or if at least one subject experiences any of the three safety events below (whichever occurs earlier):

1. Non hematologic adverse event grade  $\geq 2$ 

- 2. Hematologic adverse event grade ≥ 3 including anemia, neutropenia, leukopenia, thrombocytopenia, and lymphopenia
- 3. DLT

# Enrollment of subjects at each dose level in the multiple subject cohorts will be staggered by at least 3 days.

AMG 562 will be administered as IV infusions at weekly intervals. If no DLTs are observed, the dose escalation will continue to the next planned dose cohort as planned. Once a subject experiences a DLT, the dose for the subsequent cohorts will be decided by the DLRT after evaluating all available safety, laboratory, and PK data as well as the recommendation from the BLRM. Subsequent dose escalation will be limited to 2-fold increases or lower after a subject experiences a DLT or  $\geq$  2 patients experience a grade  $\geq$  2 adverse event.

The DLRT may also alter the dosing schedule (dosing interval) for subsequent cohorts. The changes to the dosing schedule may also include the implementation of step-up dosing for future cohorts based on tolerability as observed in the clinical and pharmacological data.

The DLT evaluation period will be at least 28 days for all cohorts. The DLT evaluation period may also be extended to assess events starting within the DLT window. Any adverse event occurring outside the DLT window that meets the DLT definition and is determined by the investigator to be possibly related to AMG 562, and seen more frequently, or is more severe than expected, or is persistent despite appropriate management, can be determined to be a DLT upon unanimous decision by the DLRT after review of the event and all available safety data. A DLRM will be conducted after the subjects in each dose cohort have had the opportunity to complete the DLT evaluation period. The DLRT may also convene at any time to review safety data if deemed necessary.

Subjects who complete the DLT period may proceed to a higher dose level for the next dosing (intra-subject dose escalation) once this higher dose level has been deemed safe by the DLRT and after consultation with the Amgen medical monitor if:

- No DLT has been reported for this subject during or after completion of the DLT period
- The subject has not experienced any ≥ grade 2 adverse events (deemed treatment related by the investigator) during treatment

DLTs experienced by subjects after completing the DLT period will be considered in the BLRM design to account for any late onset toxicity.

Dose exploration will continue until any of the following events:

- The highest planned dose level is determined to be safe and tolerable (minimum of 6 treated subjects)
- An MTD is identified where BLRM repeats the recommendation of a dose level (minimum of 6 treated subjects)
- If fewer than 6 subjects are treated at the MTD/RP2D, additional subjects may be enrolled to confirm safety and tolerability.

Further details can be found in protocol section 3.

#### Step-up Dosing (Estimation of initial dose and target dose)

Step-up dosing will be explored to prevent first dose effects like CRS or neurologic events that have been observed with other BiTE antibodies. It will be introduced when two or more DLTs consistent with potential first-dose effects are observed in one cohort. Further details can be found in protocol section **3**.

#### Part 2: Dose Expansion

Upon completion of the dose exploration part of the study, up to approximately 55 additional subjects will be enrolled in the dose expansion part to gain further clinical experience, safety and efficacy data for AMG 562 in subjects with relapsed / refractory DLBCL. The dose to be evaluated will be at or below the MTD estimated in the dose exploration cohorts. Additional expansion cohorts may be enrolled to evaluate alternative dose levels, or biologic subsets, or other disease entities included in the dose exploration. A final estimate of the MTD and RP2D will be evaluated and confirmed utilizing all DLT-evaluable subjects from the dose exploration and the dose expansion cohorts. The DLRT will be convened in the dose expansion part of the study to review efficacy data (with recruitment ongoing). Additionally, the DLRT will review safety data in the expansion part, after the first **15** subjects were enrolled and had the opportunity to receive at least five weeks of treatment (with recruitment ongoing). The guidelines for futility due to insufficient efficacy are in Table 2 in the protocol. Ad hoc meetings may be convened at any time by the DLRT to review the safety data if deemed necessary.

## 3.2 Sample Size

It is anticipated that approximately 85 subjects will be enrolled in this study. Approximately 30 subjects will be enrolled in the dose escalation cohorts and up to 55 additional subjects will be enrolled in the dose expansion cohort. The sample size in the dose escalation is based on practical considerations and is consistent with conventional oncology studies with the objective to estimate the MTD. With 3 subjects per cohort, there is a 27-70% probability of observing at least one DLT if the true DLT rate is 10-33% and with 4 subjects per cohort, there is a 34-80% probability. In the dose expansion cohort, 55 subjects will provide a 43% probability of observing at least one adverse event with a true 1% incidence rate and 94% probability of observing at least one adverse event with a true 5% incidence rate. With 55 subjects and a 40% ORR, the expected 90% CI would be 29% to 52%.

#### 3.3 Adaptive Design

A two-parameter Bayesian Logistic Regression Model (BLRM) is used to guide dose exploration. The MTD target Toxicity Probability Interval (TPI) for DLT is (0.20, 0.33] and TPIs of (0.33, 0.60] and (0.60, 1.00] are defined as excessive and unacceptable, respectively. The design seeks to identify a dose most likely to have a DLT rate in the target TPI, but with overdose control that limits the possibility the dose has an excessive or unacceptable DLT rate (Babb et al, 1998). The probability of a DLT at dose level di is assumed to follow a Bernoulli distribution with probability pi where the logit of pi increases linearly with the log of the standardized dose in the following 2-parameter logistic model:

 $\log [p_i / (1-p_i)] = \log (p_i) = \log [a] + \exp(\log [b]) \log (d_i / d_{ref})$ 

where a and b are random variables and  $d_{ref}$  is 1 of the planned dose selected as the reference dose.

A bi-variate normal prior distribution (Neuenschwander et al, 2008) was selected for theta = (log a, log b) where the probability that the true DLT rate is  $\leq$  0.40 at the lowest planned dose is **and** the probability the true DLT rate is  $\leq$  0.05 at the reference dose is 0.05. These values were selected such that pi is 0.01 for the starting dose and 0.40 for the reference dose (**m** µg).

The operating characteristics of the two-parameter BLRM design were evaluated via simulation using EAST version 6.4.1. The cohort size was fixed to 3 or 4 subjects. All simulated studies start with the multiple subject cohorts. The initial multiple subject dose level is  $\mu$ g and subsequent doses were selected based on the following rules:

After each cohort, the next dose is the one with the highest probability of the target TPI, but with a less than 0.40 probability of an excessive or unacceptable TPI.

Dose exploration will continue until any of the following events.

- The highest planned dose level is determined to be safe and tolerable (minimum of 6 treated subjects)
- An MTD is identified where BLRM repeats the recommendation of a dose level (minimum of 6 treated subjects)
- If fewer than 6 subjects are treated at the MTD/RP2D, additional subjects may be enrolled to confirm safety and tolerability.

#### 4. Covariates and Subgroups

#### 4.1 Planned Covariates

Not applicable.

#### 4.2 Subgroups

#### No Subgroup analysis planned due to early termination of the study.

#### 5. Definitions

#### Age at Enrollment

Subject age at enrollment will be determined using the age in years reported in the clinical database.

#### Baseline

Unless otherwise specified, the baseline value for parameters/assessments scheduled to be performed on the same day as the first administration of AMG 562, is the last value

measured before the first administration of AMG 562 on that day. For parameters/assessments not scheduled to be performed (or scheduled but not performed) on the same day as the first administration of AMG 562, the baseline value is the value from the screening period measured closest to the day of first administration of AMG 562. In the event that multiple assessments are done on the same day as the first administration of AMG 562 and there is no time associated with the assessments, the value associated with the last clinically planned event before the first administration of AMG 562 will be used as the baseline value

The baseline ECG is defined as the mean of all pre-dose assessments from cycle 1 day 1. The mean of the values within a triplicate will be calculated and used in the analysis. Where an ECG is missing within a triplicate, all available data will be averaged for that time point.

#### **Body Mass Index (BMI)**

Body Mass Index should be calculated using the following formula:

BMI  $(kg/m^2)$  = weight  $(kg) / [height (cm)/100]^2$ 

## Bazett-corrected QT Interval (QTcB)

The Bazett correction will be calculated from the investigator reported QT (msec) and RR interval (msec), as follows:

QTcB=QT/(RR/1000)1/2

## Change From Baseline

Change from Baseline is the arithmetic difference between post-Baseline and Baseline.

## **Disease-related Event (DRE)**

Disease-Related Events are events (serious or non-serious) anticipated to occur in the study population due to the underlying disease including Lymphadenopathy, Disease progression, Fatigue, Weight decreased and Night sweats.

## Duration of Response (DOR)

DOR is calculated only for subjects who achieve a response (CMR or PMR). The duration will be calculated from the date a response is first achieved until the earliest date of a disease assessment indicating a disease progression or death, whichever occurs first. Subjects who do not have a relapse event will be censored on their last disease assessment date. If the last disease assessment date is after the date that triggers the analysis, the subject will be censored at the analysis trigger date.

Censoring rule for duration of response: Data for responders who are alive and without disease progression are censored at the time of last evaluable disease assessment by PET-CT scan.

#### Dose Limiting Toxicity (DLT)

A DLT is any of the events described in section 6.2.1.3 of the protocol, occurring in a subject during the DLT window unless clearly attributable to causes other than AMG 562 treatment.

## **DLT Evaluable Period**

DLT evaluable period will be at least 28 days for all cohorts and may be extended to assess events starting within the DLT window.

## Enrollment Date

Enrollment Date is defined as the date of enrollment collected on the CRF.

#### End of Treatment

Defined as the last assessment for the protocol-specified treatment phase of the study for an individual subject.

## End of Study (Individual Subject)

The end of study date for an individual subject is the last day that protocol-specified procedures are conducted for that subject. The end of study date for an individual subject is recorded on the end of study CRF page.

#### End of Study (primary completion)

It is defined as when the last subject is assessed or receives an intervention for the purposes of final collection of data for the primary analysis.

## End of Study (End of Trial)

It is defined as when the last subject is assessed or receives an intervention for evaluation in the study (ie, last subject last visit), following any additional parts in the study (eg, LTFU).

#### End of Follow-up

It is defined as when the last subject completes the last protocol-specified assessment in the study.

## Fridericia-corrected QT Interval (QTcF)

The Fridericia correction will be calculated from the investigator reported QT (msec) and RR interval (msec), as follows:

#### QTcF=QT/(RR/1000)1/3

## Long Term Follow Up (LTFU)

Following the SFU visit, there will be a LTFU period for clinical evaluation of disease status and survival. Subjects will be followed via on-site visit every 6 weeks (± 3 days) for assessments of disease status and documentation of anti-lymphoma treatment until progression of disease. From this time point onwards subjects will be followed every 3 months (± 2 weeks) for survival and anti- lymphoma treatment (on-site visits are not required, if needed also interrogation of public databases is acceptable). Subjects will be followed for a maximum of 2 years from the first dose of AMG 562, or until subject death, whichever occurs first.

## Maximum Tolerated Dose (MTD)

An estimate of the MTD will be made based on a Bayesian Logistic Regression Model (BLRM) utilizing all DLT-evaluable subjects from the dose exploration and dose expansion cohorts. Based on the BLRM, the MTD is defined as the dose with the highest probability of a DLT rate between the targeted toxicity (0.2, 0.33) interval while controlling the probability of excessive and unacceptable toxicity below 40%.

## Investigational Product

The term 'investigational product' is used in reference to AMG 562.

## **Objective Response**

**Objective** response is defined as a tumor response assessment of either complete metabolic response or partial metabolic response determined by Lugano Classification.

## **Objective Response Rate**

ORR is defined as the incidence rate of a confirmed CMR or PMR while on study as defined by Lugano Classification.

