#### 6.8 Excluded Treatments, Medical Device Use, and/or Procedures During Study Period

The following treatments and/or procedures are excluded during the treatment period of the study (until SFU):

- any antitumor therapy other than AMG 562, such as:
  - cytotoxic and/or cytostatic drugs
  - radiation therapy (with the exception of radiotherapy for palliative care such as bone pain; this is only permitted after discussion with Amgen Medical Monitor)
  - immunotherapy
- any other immunosuppressive therapies (except for the management of acute, treatment–related toxicities such as transient – ie, for up to 2 weeks - use of corticosteroids and tocilizumab)
  - high-dose corticosteroid therapy (dexamethasone > 24 mg/day or equivalent) is only allowed for up to 7 days
- any other investigational agent
- treatment with growth factors, IV antibiotics, antivirals, or antifungals during DLT window unless discussed with the Amgen Medical Monitor
- treatment with medications known to cause QTc interval prolongation unless approved by the Amgen Medical Monitor (see Appendix E)
- treatment with medications that are CYP450 substrates with a narrow therapeutic index in cycles 1 and 2 unless approved by the Amgen Medical Monitor (see Appendix G for examples). In case use of these substrates is approved, appropriate monitoring for potentially increased toxicity should be implemented.
- any major surgery
- 7. STUDY PROCEDURES
- 7.1 Schedule of Assessments

Page 77 of 158

#### Table 8. Schedule of Assessments for Screening and Treatment Cycle 1

[figure not shown]
Footnotes defined on last page of this table

Page 1 of 4

CONFIDENTIAL

Page 78 of 158

#### Table 8. Schedule of Assessments for Screening and Treatment Cycle 1

Footnotes defined on last page of this table

Page 2 of 4

AMGEN

CONFIDENTIAL

SCR Treatment Period (Cycle 1) -21 to -1 110 16 17 20 23 Cycle Day 1b 0 0 4 8a 15a 22ª Relative to start of infusion Predose Predose Predose Predose Hours 6 5 220 5 200 5 20 110 116 116 120 120 0 0 000 $\overline{}$ ဖစ  $\sim \sim$  $\sim$ **BIOMARKER ASSESSMENTS (continued)** PK ASSESSMENTS Х\* хх Х\* AMG 562 PKn, r Х Х Х Х Х Х\* X\* Х х х хх Х Page 3 of 4

# Table 8. Schedule of Assessments for Screening and Treatment Cycle 1

Footnotes defined on last page of this table

25

Х

	SCR				Tre	eatment Period (	(Cycle 1)			
Cycle Day	-21 to -1		1 b	3 3	8 a	9 10 11	15ª	16 17 18 20	22ª	23 24 25

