Page 2 of 4

Footnotes defined on last page of this table

Page 3 of 4

Approve

Page 93 of 158

			Treatment Period	(Cycle 3 a	nd following)					EoT SFU	LTFU°
Cycle Day	1 b	3 0 4	8 a	9 10 11	15ª	16 17	18	22ª	23 24 25		Up to
Hours	Relative to start of infus	ion	Relative to start of	infusion	Relative to st		sion	Relative to s	tart of infusion		2 yrs after 1 st
	Pre 0 0 0 0 0 12 12 12 12	20 24 72 72	0 6 8 12 12	24 48	Pred 6 6 12	24 48	1	Press 4 0 4 0 4 6 6 6 6 6 6 6 6 6 6 6 6 6 6 6	24 48 48		IP dose
BIOMARKER AS	SESSMENTS (Continued)										
PK ASSESSME	ITS										
AMG 562 PK p, t	x x	X			×			x		x x	
DISEASE ASSE	SSMENTS and RADIOGRAPHIC	ASSESSMENT	rs								
PET/CT q										х	
BM aspirate/ biopsy i			<	at EO1	to confirm CR I		>				

Page 4 of 4

Page 94 of 158

Ab = antibody, AE = adverse event, BM = bone marrow, chem = chemistry; con meds = concomitant medications, CR = complete response, CRS = Cytokine Release Syndrome, ctDNA = circulating tumor DNA, CT = computed tomography, demo = demographics, DRE = disease-related event, ECG = electrocardiogram, ECOG = Eastern Cooperative Oncology Group, EOT = end of treatment, Expl = exploratory, hem = hematology, Ig = immunoglobulins, LTFU = long-term follow-up, MRD = minimal residual disease, MRI = magnetic resonance imaging, neuro = neurological, NGS = next generation sequencing, ox = oximetry, PB = peripheral blood, PD = progressive disease, periph = peripheral, PK = pharmacokinetics, PR = partial response, SAE = serious adverse event, SFU = safety follow-up, a The Dose Level Review Team may decide to change timing of D8/D15/D22 within a window of ± 1 day. In this case, timing of the following visits would be adjusted accordingly.

b In case of step-dosing, the subsequent treatments will be at weekly intervals after the target dose is administered.

c LTFU via on-site visit every 6 weeks until progression of disease. Afterwards, LTFU frequency will be 3 months for collecting information on survival and subsequent anti-lymphoma treatment only, without the requirement for on-site visitsThe procedures or assessments as mentioned in section 7.2.4 are applicable only if on-site visits apply.

d See Section 6.2.1.1 for details on hospitalization requirements.

e See Section 9.2.2.1 and Section 9.2.2.3 for SAE reporting requirements during LTFU.

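### The on-study response window has no cut-off at new anti-lymphoma therapy, so a confirmed CMR or PMR reached after such therapy, in a subject without progression, can be counted for AMG 562

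*SAP*

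**What the plan says.** - **Response window.** SAP section 5, Objective Response Rate: "ORR is defined as the incidence rate of a confirmed CMR or PMR while on study as defined by Lugano Classification". The neighbouring Objective Response entry says "response is defined as a tumor response assessment of either complete metabolic response or partial metabolic response determined by Lugano Classification" and gives no window and no confirmation requirement. SAP 9.5.2 gives no window for best overall response.
- **How long a subject is on study.** The SAP list of abbreviations ends the study for a subject at withdrawal of full consent or when the subject "completes the safety follow-up visit or long-term follow up [whichever is later] or death". On length, SAP section 5 (LTFU) says "Subjects will be followed for a maximum of 2 years from the first dose of AMG 562, or until subject death".
- **What follow-up collects.** Until progression, on-site visits take place every 6 weeks "for assessments of disease status and documentation of anti-lymphoma treatment until progression of disease". Protocol 7.2.4 says the same and lists disease assessments among the procedures. After progression, a footnote to Protocol Table 11 reads: "Afterwards, LTFU frequency will be 3 months for collecting information on survival and subsequent anti-lymphoma treatment only".
- **Other therapy.** Protocol 6.8 excludes other antitumor therapy during treatment, until the safety follow-up visit. Radiation is excluded too, but "with the exception of radiotherapy for palliative care such as bone pain", after discussion with the medical monitor.
- **Time-to-event endpoints.** For DOR the SAP says: "Data for responders who are alive and without disease progression are censored at the time of last evaluable disease assessment by PET-CT scan". PFS is censored at the last PET-CT assessment. Neither rule mentions subsequent therapy.

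**The concern.** In a single-arm trial, ORR and CR rate carry the evidence of activity. They can be read that way only if a counted response could have come from AMG 562. Here the window closes at the end of study participation, while the plan expects other lymphoma therapy to start, and to be recorded, inside that window.

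The subjects at issue are foreseeable. Protocol 6.2.1.4.4 lists several reasons to stop AMG 562 that are not progression, such as repeated or severe CRS, grade 4 non-hematologic events, more than one dose reduction, and a need for alternative therapy. Such a subject stays under disease assessment. If a later treatment produces a CMR or PMR, the definition as written does not say that it is not an AMG 562 response. The programmer of the tables would have to decide, with open-label data in view.

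The matter is still live. SAP 9.5.2 keeps ORR, best overall response, DOR and PFS after the early termination, and SAP 7.2 says the primary snapshot holds data up to long-term follow-up for all subjects but one.

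**Working it through.** **1. Is there a cut-off anywhere?** These places could hold one: Protocol 10.1.4 and 10.5.3.2; SAP section 5 (DOR, Objective Response, ORR, PFS); SAP 8.3; SAP 9.5 and 9.5.2; SAP section 10. The missing-data rule makes a subject without any assessment a non-responder. None of the places deals with a response after new therapy or after radiotherapy to a lesion.

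**2. Can a scan fall after new therapy?** Inputs: scans at weeks 5, 15, 25 and at end of treatment if that is week 35 or later (Protocol 3.1); a scan 14 (+3) days after the last dose on discontinuation (Table 11 footnote); safety follow-up 30 (+7) days after the last dose. Protocol 7.3.12.3 equates week 5 with cycle 2 day 1, that is day 4 × 7 + 1 = 29. So week 15 starts on day 14 × 7 + 1 = 99 and week 25 on day 24 × 7 + 1 = 169.

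Example: last dose on day 22, stopped for toxicity without progression.

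| Event | Day |
|---|---|
| Discontinuation scan | 22 + 14 = 36 to 22 + 17 = 39 |
| Safety follow-up; bar on other therapy ends | 22 + 30 = 52 to 22 + 37 = 59 |
| Week 15 scan | 99 |
| Week 25 scan | 169 |

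The discontinuation scan precedes any permitted new therapy. The week 15 scan comes 99 − 59 = 40 to 99 − 52 = 47 days after the bar ends. Protocol 3.1 does not limit the week 15 and week 25 evaluations to subjects still on AMG 562. Protocol 7.2.2, however, lists them under the treatment period, so such a scan is possible but not clearly required. The 6-weekly follow-up assessments are a second route; their imaging content is not specified.

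**3. Size.** The plan's own figure first: with 22 of 55 responders (40%), the Clopper-Pearson 90% interval is 28.9% to 52.0%, which matches the stated 29% to 52%. No stated figure is wrong.

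One extra counted responder changes ORR by 1/N:

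- N = 55 (planned Part 2): 1/55 = 1.8 points. For example, 21/55 = 38.2% (90% CI 27.2 to 50.2%) becomes 22/55 = 40.0% (28.9 to 52.0%).
- N = 30 (planned Part 1): 1/30 = 3.3 points. For example, 2/30 = 6.7% (1.2 to 19.5%) becomes 3/30 = 10.0% (2.8 to 23.9%).
- N = 10 (assumed, for a study stopped early): 1/10 = 10 points. For example, 2/10 = 20% (3.7 to 50.7%) becomes 3/10 = 30% (8.7 to 60.7%).

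The responder counts are illustrations. The documents give neither the number treated nor the number of responses after new therapy.

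**4. Direction.** A missing cut-off can add a responder or raise a PMR to CMR; it cannot remove a response. A PMR upgraded in this way changes the CR rate but not ORR.

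**The case against.** The strongest reply is that the route is narrow, and most of that reply stands.

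- CMR and PMR are PET findings under Protocol Appendix D. The planned discontinuation scan comes before new therapy is permitted. Table 11, as it can be read, shows no PET/CT mark for long-term follow-up, though the table may have been damaged in extraction.
- Progression already closes disease assessment, so subjects who change therapy because of progression are not exposed.
- ORR is secondary, SAP 2.2 says all analyses are descriptive, and subject-level efficacy listings are planned.
- Letting DOR and PFS run through new therapy is a legitimate choice of estimand. Censoring at new therapy can itself be informative.

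Three stronger readings are tempting, and the documents support none of them:

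- *Every response after new therapy counts.* The ORR entry asks for a confirmed response, and only subjects without progression remain under assessment. Confirmation gives limited protection, because it is not defined and the Objective Response entry does not ask for it.
- *Such responses have been credited to AMG 562.* The documents show only that they could be.
- *DOR can be carried to the two-year limit of follow-up.* DOR is censored at the last evaluable PET-CT, and with no PET/CT clearly scheduled in long-term follow-up that date may come much earlier.

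The reply does not supply a rule for a subject who does have a qualifying scan after new therapy.

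**Conclusion.** The gap is real and of limited reach. Read literally, the ORR definition can credit AMG 562 with a confirmed response that followed another therapy, in subjects who stopped without progression. Best overall response has the same gap. How many subjects this affects is unknown and probably small. The effect is 1/N per case, 1.8 points at 55 subjects and 3.3 at 30, and for ORR and CR rate it always favours the drug. These figures assume that the affected subject had not already responded and that a later scan was done and counted as confirmed.

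This should be fixed before the efficacy tables are produced, but it does not undermine the trial: safety is primary and efficacy is descriptive. The firm part concerns ORR and best overall response. For DOR and PFS the documents leave an estimand choice unstated, which is best met by showing both versions. Palliative radiotherapy is a lesser form of the same gap, since nothing shows that it would be given to a lesion that decides response.

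**What to change.** - In SAP section 5 (Objective Response Rate), replace the on-study window with: from first dose of AMG 562 until the earlier of progression or start of subsequent anti-lymphoma therapy. Add the same window to the Objective Response entry and to best overall response in SAP 9.5.2.
- State that a response in a lesion is not credited after radiotherapy to that lesion.
- Report DOR and PFS both as now defined and with censoring at the last evaluable assessment before subsequent therapy.

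The cost is SAP wording and one extra version of two analyses. Sample size and the stated figures do not change. Protocol 7.3.5 and the long-term follow-up column of Table 11 already collect subsequent anti-lymphoma therapy, including its start date. The radiotherapy rule may need a data query, because the concomitant-therapy items in Protocol 6.5 do not include the treated site. The downside is that ORR or CR rate may come out slightly lower.
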